#### **6. Feasibility and Feedback**

**Outcome ascertainment** - Using compliance data and parent reporting, we will also determine if the intervention is feasible for this population. Compliance with treatment is already being measured. In addition, after completing the 5 day intervention at Day 6, parents will be asked several questions about the ease of the cloth and ointment use as well as their comfort level and other feelings about the treatment. During the follow-up testing of parents, we will ask for any comments, suggestions or concerns from the parents about their general experience as a participant in the study. This data will be both quantitative and qualitative and can help determine if the intervention is feasible for future use. The study team may on occasion audio record responses to these questions.

#### **7. Attitudes and Behavior**

**Outcome ascertainment** – In order to examine the impact of *S. aureus* education and knowledge of *S. aureus* colonization, all consented parents will be asked to complete a follow-up questionnaire. The questionnaire will assess differences in behavior between ineligible parents (negative for *S. aureus*) and eligible parents (at least one parent positive for *S. aureus* and enrolled in study). In the questionnaire, parents will be asked about their interactions and behaviors with their newborns in the NICU, whether their hand hygiene and/or bathing routines have changed, and about modifications made to medication use over the course of the four weeks since their initial screening visit.

## **6. Risks and Benefits**

### **A. Potential Risks**

The risks for this study are minimal. There is a very small risk of bleeding associated with swabbing mucosal membranes; however, our institution has a long standing history of obtaining nares surveillance cultures for *S. aureus* and peri-anal surveillance cultures to detect vancomycin resistant enterococci without any reported adverse events. Throat swabs can make people gag but are routinely performed during clinical evaluations of pharyngitis without adverse events. Standard precautions will be applied for protection of the research team member during specimen collection. All parent swabs will be collected in a private room. Groin and peri-anal swabs will be self-collected by parents following instructions from the study team. If the parents prefer, the groin and peri-anal swabs can be collected by a study team member. A gown will be provided for the parent to protect modesty and privacy during collection if applicable.

This decolonization procedure is widely used in individuals with *S. aureus* colonization in certain settings such as pre-operative, recurrent infections, and those in the intensive care unit. This treatment has been well tolerated in all populations, with rare adverse events. Allergic reactions to mupirocin and/or chlorhexidine are uncommon. Patients with known allergy to any product ingredient will be excluded from the study. All agents are FDA approved for the target population and we have received an FDA exemption from IND. A number of recent studies have applied decolonization to households rather than just individuals, as close contacts can serve as reservoirs for recurrent colonization after treatment. Based on reports that treating households versus just individuals may have a greater impact on *S. aureus*, we have decided to treat both parents even if one is not colonized. To protect parent's privacy and prevent potential feelings of guilt or one parent blaming the other, we will not disclose discordant results to parents. Therefore, care providers will not know if a particular parent is colonized simply based on enrollment in the study, as it might be "the other parent" that is colonized.

**Mupirocin Ointment Possible Adverse Effects:** Local adverse effects may be associated with mupirocin application. Mupirocin ointment may cause itching, pain, stinging, and burning. Local effects from the nasal formulation have included epistaxis, rhinitis, taste perversion, pharyngitis, burning, and cough. Gastrointestinal side effects have included nausea (1.1%), abdominal pain (<1%), and diarrhea (<1%). Dry mouth has been reported with mupirocin nasal (<1%). Nervous system side effects associated with intranasal mupirocin have included headache (9%). Dizziness has been reported with mupirocin ointment (<1%). Ocular side effects associated with mupirocin nasal ointment have included blepharitis (<1%).

**Chlorhexidine Gluconate-impregnated Cloths Possible Adverse Effects:** The soap may cause burning and dryness of the skin. It may cause burning of the eyes, but it's not recommended to be used above the neck. Skin erythema and roughness, dryness,

sensitization, allergic reactions are possible, but rare.

## **B. Protection against Risks**

**Protection against loss of information:** We will institute strict procedures to maintain confidentiality. All patients will be assigned a study identification number. We will maintain a master list of patients with unique study identifiers. The master list will be maintained on a password protected computer or institutional network drive. Data will be entered into REDCap (<http://www.project-redcap.org>) which is a secure, web-based application designed exclusively to support data capture for research. The Johns Hopkins University is a member of the REDCap consortium and this application is freely available to consortium members. REDCap provides: 1) an intuitive interface for data entry (with data validation); 2) audit trails for tracking data manipulation and export procedures; 3) automated export procedures for seamless data downloads to common statistical packages (SPSS, SAS, Stata, R); 4) procedures for importing data from external sources; and 5) advanced features, such as branching logic and calculated fields. To maximize quality control, staff will be trained by the PI in all data collection and entry procedures. The PI will have access to all data upon entry into REDCap. The research coordinator will monitor data collection by checking data for completeness. All research staff will be instructed regarding the security of data and will maintain the highest ethical standards in protocol adherence and data collection. After all data are collected, analyzed, and published, linkage between patients and their unique identifier will be destroyed in accordance with local regulations with the exception of data that have been collected for hospital surveillance activities. During the course of the study, information collected will not be disclosed to anyone other than the study personnel. No sensitive information will be collected. Following completion of each qualitative interview, all audiotapes (digital recordings) will be transcribed and marked with the session title and each subject's SID number. No identifying information will appear on the label of the media. All transcribed media will be stored on a secure Johns Hopkins server. Audio recordings with identifiers will be destroyed after being transcribed.

**Protection against adverse events from treatment:** As discussed above, treatment of *S. aureus* colonized individuals with intranasal mupirocin and chlorhexidine gluconate-impregnated cloths is routinely performed in many clinical settings. Very rare cases of anaphylaxis have been reported. Parents will be given written and verbal instructions for proper use. The research team will contact parents daily to review compliance with treatment, to answer questions, and to monitor for adverse events. Safety data including expected and unexpected events will be provided to the DSMB for review. Any unexpected events will be submitted immediately to the IRB.

The study team recognizes that subjects may seek advice about issues beyond the scope of this study and will refer all non-study related health issues to the patient's treating clinician.

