(greater than or equal to or less than 1500g). Use of varying block sizes (4, 6 and 8) will decrease the risk of imbalance. Neonates of multiple gestations and their parents will be randomized as a single family unit. Investigators and participants will be masked to treatment assignment. The treating clinicians of the neonates will be masked to treatment assignment. The investigational drug pharmacy will use the randomization sequences to prepare supply kits. As subjects are enrolled, they will receive the next kit in sequence based on the study site and birth weight of the neonate. Each kit will contain either active drug or placebo. Active chlorhexidine-impregnated cloths, active mupirocin ointment and their respective placebos will be identified only by lot numbers, and the respective lot numbers will only be known to the investigational drug pharmacist.

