**Reducing the risk of bias in outcome ascertainment:** Clinicians will continue to send cultures to evaluate neonates for possible infection as part of routine clinical management. The primary care providers in the NICU will not participate in the study and will be masked to the parent-neonate pair assignment. Maintaining masking of the clinicians will reduce the chance that practices for obtaining clinical cultures will differ between the two groups.

The **observation period, or survival time**, is the time that a neonate is at-risk of concordant *S. aureus* acquisition. We will calculate survival time as 1) the interval

between randomization and the date of final culture (either at time of final surveillance culture or at time of discharge culture) for neonates who did not acquire concordant *S. aureus* and 2) the interval between randomization and date of first positive culture for neonates that acquire concordant *S. aureus*.

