**2. Neonatal *S. aureus* infection as determined by cultures collected during routine clinical care**

**A *S. aureus* infection** will be defined using criteria established by the Centers for Diseases Control and Prevention National Healthcare Safety Network and will be determined using results of cultures sent during routine clinical care (other than surveillance cultures).

**Secondary outcome ascertainment** - Two study team members that are blinded to treatment assignment will review all clinical cultures for *S. aureus* during the treatment and control period and determine if the culture represents an infection due to *S. aureus*. A third study team member will review the case in the event of discordant results.

The **observation period, or survival time, is the** time a neonate is at-risk of *S. aureus* infection. We will calculate survival time either by 1) the interval between randomization and the date the neonate is discharged from the NICU or death for neonates who did not develop a *S. aureus* infection or 2) the interval between randomization and date of positive culture for neonates that develop *S. aureus* infection. Neonates will not be included if they have an infection after meeting the primary outcome of concordant *S. aureus* colonization or the secondary outcome of neonatal acquisition of *S. aureus*.

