##### **Plan for Parents Testing Positive for *S. aureus* and disclosure of follow-up results:**

Upon enrollment, all subjects will be provided a brief structured orientation and education session regarding *S. aureus* by a member of the research team. All patient questions will be answered and educational handouts will be provided with references for additional information. Part of the informed consent will include an understanding that parents will be made aware of their *S. aureus* colonization status. If either or both parents are colonized, parents will be informed that one or both parents are colonized,

but we will not share which parent to protect confidentiality. By participating in the trial, others may also become aware that one of both of the parents are colonized simply by their participation in the trial. We will explain that approximately 30% of healthy adults are colonized with *S. aureus*. We do not take special precautions or treat parents differently that are colonized with *S. aureus*. Additionally, we will enroll both parents even if only one parent is colonized, which will aid in protecting the privacy of participants as care providers will not know if a particular parent is colonized simply based on enrollment in the study, as it might be “the other parent” that is colonized.

Once parents are randomized to an assigned treatment, they will continue to be screened for *S. aureus* colonization throughout the study. The results of subsequent testing will not be made available to the parent. Disclosing subsequent testing results may lead to unmasking of the study. Parents will be informed that these results will not be available until the study is complete and the randomization code is un-blinded for data analysis. Parents will be provided with a means to contact the study team to learn their testing results and/or randomization group.

Parents with discordant culture results should not become aware of each other’s colonization status. To decrease or eliminate guilt issues, the study team will not disclose which parent is colonized and will educate parents on the ubiquity of *S. aureus* and emphasize that parents are only one possible source of transmission.

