#### ***S. aureus* strain typing:**

1. Strains of *S. aureus* will be compared using pulsed-field gel electrophoresis (PFGE) analysis. DNA will be extracted by standard methods and the restriction enzyme digested using *Sma*1. A *Staphylococcus aureus* subspecies NCTC 8325 will be used as a control strain with a molecular weight ladder at the beginning and end of each gel. Control isolates, including all USA PFGE strain types, will be used for comparison. Using 1% pulsed-field certified agarose gel (BioRad Laboratories, Hercules, CA) electrophoresis will be performed on the CHEF-DR III (BioRad Laboratories, Hercules, CA) with 0.5X TBE buffer at 14°C. The gels will be stained with ethidium bromide and scanned using a molecular analysis fingerprinting software (Fingerprinting II Version 3.0; BioRad Laboratories, Hercules, CA). If PFGE using standard enzymes was unable to yield an interpretable fingerprint, PFGE was then performed using an alternative method utilizing Achromopeptidase (Wako Bioproducts, Richmond, VA) as the lysis enzyme in order to obtain an interpretable fingerprint. Gel images will be stored and within and between run comparisons will be performed for each group of tested isolates. Isolates will be considered related if their patterns have ≤3 band differences. Isolates with >3 band differences will be considered epidemiologically different strain types.
2. Alternative *S. aureus* strain typing method: Because some *S. aureus* strains are genetically similar by PFGE, such as strain USA300, validation of highly prevalent and concordant strains will be carried out using a separate assay such as a PCR assay coupled with electrospray ionization-mass spectrometry (PCR/ESI-MS), whole genome or next generation sequencing, or multi-locus sequence typing. Isolates with no band differences will be considered identical, but those with 1-3 band differences will be considered for additional testing based on strain prevalence.
3. If strains could not be distinguished by PFGE analysis, multi-locus sequence typing (MLST) will be performed using whole genome sequencing. After DNA extraction, a sequence library will be generated using the Nextera DNA Library Preparation Kit and sequenced by Miseq (Illumina Inc, San Diego, CA). Sequenced fragments will be assembled using SPAdes and aligned to reference

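### Parents' follow-up cultures, which the protocol itself says may unmask the study, are not kept from the masked PI, the infection reviewers or those choosing isolates for further typing

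*Combined protocol and SAP*

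**What the plan says.** - **Masking.** Section 4.C.6 (Allocation): "Investigators and participants will be masked to treatment assignment". Treating clinicians are masked too, and only the investigational drug pharmacist can decode the lot numbers.
- **Parents' follow-up cultures.** Section 6.D: "The results of subsequent testing will not be made available to the parent". The reason follows: "Disclosing subsequent testing results may lead to unmasking of the study". Parents may learn the results once the study is complete and the code is opened.
- **Data access.** Section 6.B: "The PI will have access to all data upon entry into REDCap". The research coordinator checks data for completeness. The same section limits access from outside: "information collected will not be disclosed to anyone other than the study personnel".
- **Infection outcome.** Section 5.B.2: "Two study team members that are blinded to treatment assignment will review all clinical cultures". A third team member reviews disagreements.
- **Strain typing.** Section 5.A compares the neonate's strain with the parent's screening isolate and treats up to three band differences as related. Section 7.B adds a second assay for some pairs: isolates with no band differences count as identical, but "those with 1-3 band differences will be considered for additional testing based on strain prevalence".
- **Withdrawal.** Section 4.C.8 allows withdrawal at the investigator's discretion for safety, behavioral or administrative reasons.

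**The concern.** The protocol identifies a route by which the arm could be inferred and closes it expressly for one masked group, the participants. For the other masked group, the investigators, it states open access. Parents on active treatment are expected to clear *S. aureus* more often than parents on placebo, which is one of the secondary hypotheses in Section 3.D. Anyone who sees a colonized parent's later cultures can therefore guess the arm better than chance.

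What is at stake is any decision that leaves room for judgement after such a result exists: whether a clinical culture represents infection, which pairs with one to three band differences go for a second assay, and whether a subject is withdrawn. Retyping touches the primary endpoint, because a pair counted as concordant by band pattern may cease to be so if the second assay disagrees. If these choices drift with a guessed arm, the claim of double masking is weakened where it matters.

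**Working it through.** No figure in the documents is at issue, so there is none to reproduce. The check has four parts.

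**1. Who is kept from parents' post-randomization cultures?**

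| Group | Masking status | Stated rule on these results |
|---|---|---|
| Parents | Masked (4.C.6) | Withheld until the study is complete and unblinded (6.D) |
| NICU clinicians | Masked, outside the study (4.C.6, 5.A) | Covered by the bar on disclosure beyond study personnel (6.B) |
| PI | Masked as an investigator (4.C.6) | Access to all data on entry, no exception (6.B) |
| Infection reviewers | Stated to be blinded (5.B.2) | None either way |
| Those selecting isolates for a second assay | Not stated separately (7.B) | None either way |

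**2. How much does one culture tell?** Let *a* be the probability that a parent colonized at screening is culture-negative at a follow-up visit on active treatment, and *p* the same on placebo. Both are assumptions. Allocation is balanced between two arms, so each has prior probability 0.5. Guessing active after a negative culture and placebo after a positive one gives:

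- P(correct guess) = 0.5 × (*a* + 1 − *p*)
- P(active | negative) = *a* / (*a* + *p*)
- P(placebo | positive) = (1 − *p*) / [(1 − *p*) + (1 − *a*)]

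| *a* (assumed) | *p* (assumed) | P(correct) | P(active given negative) | P(placebo given positive) |
|---|---|---|---|---|
| 0.5 | 0.4 | 0.5 × 1.1 = 0.55 | 0.5/0.9 = 0.56 | 0.6/1.1 = 0.55 |
| 0.6 | 0.3 | 0.5 × 1.3 = 0.65 | 0.6/0.9 = 0.67 | 0.7/1.1 = 0.64 |
| 0.7 | 0.2 | 0.5 × 1.5 = 0.75 | 0.7/0.9 = 0.78 | 0.8/1.1 = 0.73 |
| 0.8 | 0.1 | 0.5 × 1.7 = 0.85 | 0.8/0.9 = 0.89 | 0.9/1.1 = 0.82 |
| 0.9 | 0.1 | 0.5 × 1.8 = 0.90 | 0.9/1.0 = 0.90 | 0.9/1.0 = 0.90 |

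A second culture adds little or a moderate amount: at 0.7 and 0.2, two independent results raise P(correct) from 0.75 to 0.78. Results from one family are likely to be correlated, which would reduce the gain.

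**3. Which decisions come after a result exists?** Treatment lasts 5 days, and symptoms are asked about on those days and on Day 6 (5.B.5). The first scheduled parent follow-up swab is at week 2 with a one-week window (4.D), so at the earliest about Day 14 − 7 = 7, before incubation time. Restart and relatedness decisions on the 5-day course therefore normally precede any follow-up result. The exceptions are a final parent swab in week 1, because the neonate is discharged or acquires *S. aureus* that early, and an event attributed late. By contrast, Table 1 in Section 4.D schedules a parent swab when the neonate acquires *S. aureus*. That is about when the neonate's isolate becomes a candidate for typing.

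**4. How much could retyping weigh?** The final analysis is planned at 40 events and the first interim at 20 (9.A, 9.B). One reclassified event is 1/40 = 2.5% of the total, or 1/20 = 5% at the first interim. The documents do not say how many pairs would differ by one to three bands, so no effect on the hazard ratio can be calculated.

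**The case against.** A reader might infer that the blind is open to those who judge outcomes and reactions, and that the results are hidden from parents alone. The documents do not support this.

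- The allocation code stays with the pharmacist, and a culture only shifts the probability of an arm. Section 6.D itself says only that disclosure may unmask.
- Section 6.B closes the data to everyone outside the study, and Section 5.A adds: "The primary care providers in the NICU will not participate in the study and will be masked to the parent-neonate pair assignment".
- The infection reviewers are stated to be blinded and apply external surveillance criteria. The PI is not named among them, and no section gives them parents' results.
- Concordance follows a band-count rule against the screening isolate. The stated ground for a second assay is strain prevalence, not parental clearance.
- Reaction and restart decisions mostly fall before the first follow-up swab.
- No section says when parents' follow-up results are read or entered, and the list of parent data in Section 8 does not mention them.
- A negative culture from a parent who was not colonized at screening says little, and follow-up swabs are taken only when a parent is available.

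All of this stands as a limit on the point. It does not close the gap. Custody of the code does not prevent inference from results. The confidentiality rule leaves the data open to study personnel, the group in question. A statement that reviewers are blinded to assignment does not bar them from a result that hints at it. Silence about entry dates is not a restriction.

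**Conclusion.** The point holds as an unreconciled gap. The protocol treats parents' follow-up cultures as a threat to masking, requires masked investigators, and gives the PI all data on entry. No rule keeps these results from the infection reviewers or those selecting isolates for a second assay.

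The clue is partial: about 55% to 90% correct from one culture, entirely under assumed clearance rates, with the top figure resting on an extreme pair (90% against 10%). The exposure is to infection adjudication, discretionary retyping and investigator withdrawals, and largely not to reactions or restarts. Nothing in the documents shows that anyone would see or use the results in these decisions, and no bias in the primary result can be quantified. This is a cheap improvement worth making, not evidence that masking fails.

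**What to change.** Amend Section 6.B so that parents' post-randomization culture results are held in a restricted REDCap form until database lock. Only laboratory or data staff should see it, and they should have no role in infection adjudication, isolate selection or concordance calls, withdrawal, or adverse-event attribution. State in Sections 5.B.2 and 7.B that the people in those roles do not see these results.

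Concordance uses only the screening isolate, and parents wait for their results until the study is complete, so no decision described in the protocol needs them earlier.

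The cost is a user-rights setting, a few sentences, and one shift of work. The PI, and any coordinator who holds one of those roles, cannot check these fields until lock, so the designated laboratory or data staff must do the completeness check and need enough visit information to do it.
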